4.2. Study Conduct Rationale

SEP-363856 is a central nervous system (CNS) active drug, which shows broad efficacy in animal models of schizophrenia (positive and negative symptoms) and depression. The molecular target responsible for this profile of effects has not been completely elucidated, but may include actions at 5-HT1A and trace amine-associated 1 (TAAR1) receptors. Rat electroencephalogram (EEG) studies showed that SEP-363856 dose dependently suppressed rapid eye movement (REM) sleep. In nonhuman primate functional magnetic resonance imaging (fMRI) experiments, pretreatment with SEP-363856 reduces the ketamine brain fMRI response in rhesus monkey in a pattern analogous to that observed with risperidone, supporting an antipsychotic-like profile. Together these data revealed that SEP-363856 exhibits clear, functional CNS pharmacodynamic signals in rats and nonhuman primates. Importantly, SEP-363856 was not shown to cause Parkinson's symptoms (eg, catalepsy) in preclinical models.

As of 24 September 2018, a total of 246 subjects have received SEP-363856 in 8 completed Phase 1 clinical studies (SEP361-101, SEP361-103, SEP361-104, SEP361-105, SEP361-106, SEP361-108, SEP361-111, and DA801002). An additional 199 subjects received oral doses of SEP-363856 in studies in adults with schizophrenia: Phase 2 Study SEP361-201 (safety, tolerability, and efficacy in adult subjects diagnosed with schizophrenia; clinical study report is pending), Phase 2 Study SEP361-202 (long-term safety and maintenance of effect in subjects

diagnosed with schizophrenia and Phase 1 Study DA801004 (safety, tolerability, multiple ascending dose PK, in Japanese subjects diagnosed with schizophrenia).

Evidence for target engagement and pharmacodynamic effects were demonstrated in the following studies.

- Study SEP361-103 was a randomized, double-blind, placebo-controlled, crossover polysomnography (PSG) study that investigated the effect of a single oral dose (50 mg and 10 mg) of SEP-363856 on REM sleep suppression in healthy adult male subjects. A single 50 mg oral dose of SEP-363856 suppressed REM sleep in all subjects (increased latency to REM sleep and reduced time spent in REM sleep) and increased non-rapid eye movement sleep (NREM) sleep stage 2 (N2), and NREM sleep stage 3 (N3) (deep or slow wave sleep). A single 10 mg dose of SEP-363856 also increased latency to REM sleep to a lesser extent, but did not reduce time spent in REM sleep.
- Study SEP361-104 was a randomized, double-blind, placebo-controlled, single dose study of the effects of SEP-363856 (50 mg) and amisulpride (400 mg) on blood oxygen level dependent (BOLD)-fMRI signals in healthy male and female adult subjects with high or low schizotype characteristics. FMRI was used in combination with the monetary incentive delay (MID) task to examine the single dose effects of SEP-363856 on changes in reward processing. During the anticipation/motivational phase of the MID task, SEP-363856 modulated striatum, insula and orbitofrontal cortex brain activity, similar to the fMRI effects observed with the D2 antagonist amisulpride.
- Study SEP361-106 (Part 2) was an open-label study that investigated the PK and efficacy of SEP-363856 75 mg given QD for 28 days to 16 male and female subjects with schizophrenia. Treatment demonstrated improvement in efficacy (PANSS total score, CGI-S) compared with Baseline. Furthermore, ad hoc subgroup analyses showed a significantly greater decrease from Baseline in PANSS total scores at the end of the 28-day treatment period in subjects who had less frequent hospitalizations per year of illness compared with subjects who had more frequent hospitalizations per year of illness.
- Study SEP361-108 evaluated the effects of SEP-363856 25 and 50 mg given QD for 14 days compared with placebo in 15 adult male and female subjects with narcolepsy-cataplexy. The frequency of cataplexy attacks and overall narcolepsy symptoms were assessed by the CGI-I scale. The primary objective of the study was not met, as SEP-363856 did not demonstrate separation from placebo at either dose studied (25 and 50 mg QD) for the primary endpoints (total number of cataplexy attacks and CGI-I) at the end of the 2 week treatment period. However, SEP-363856 did demonstrate suppression of REM in narcoleptic subjects (Night 1 data), which was maintained with repeated dosing (Day 14 effect on sleep onset REM periods). These data demonstrate that central activity was observed at both doses studied (25 and 50 mg QD).

Overall, across all clinical studies conducted as of 24 September 2018, SEP-363856 has been generally well-tolerated. The majority of adverse events (AEs) observed to date have been mild

4.3. Risk-Benefit Assessment

Overall across clinical studies conducted to date, SEP-363856 has been generally well-tolerated. The majority of AEs have been mild or moderate and infrequently led to treatment discontinuation. SAEs have also been infrequent and have been reported predominantly in studies conducted in subjects with schizophrenia. A single event of hypotension experienced by a normal healthy volunteer was assessed as serious. TEAEs of hypotension and orthostatic hypotension observed to date have occurred in studies of both normal healthy volunteers and in subjects with schizophrenia, have been transient, mild or moderate in intensity and the majority did not require concomitant treatment or intervention. The PK and safety profiles observed in adult subjects from completed Phase 1 and Phase 2 clinical studies supports the evaluation of flexibly-dosed SEP-363856 at 25, 50 or 75 mg/day in adult subjects with PDP.

PD is a chronic neurodegenerative disorder that affects motor control. It is the second most common neurodegenerative disease after Alzheimer's disease and affects approximately 1 million people in the US and 7 million globally. PDP has been associated with poorer quality of life, increased morbidity and mortality, and increased caregiver burden and nursing home placement (Aarsland-2000). NuplazidTM (pimavanserin), a selective 5-HT2A inverse agonist, is the first treatment approved for PDP by the US FDA. SEP-363856 has a novel mechanism of action not related to direct antagonism of the D₂ or 5-HT_{2A} receptors and may benefit patients with PDP.

4.4. Hypothesis

4.4.1. Primary Hypothesis

Treatment with SEP-363856 in subjects with PDP will result in a significant reduction in the Scale for Assessment of Positive Symptoms – Parkinson's Disease (SAPS-PD) total score at Week 6 when compared to placebo.

Let μ_{SEP} and μ_{PBO} represent the mean changes from Baseline at Week 6 in SAPS-PD total score for the SEP-363856 and placebo arms, respectively. The following hypothesis will be tested to compare the mean change values between the SEP-363856 group and placebo group at Week 6:

 H_0 : $\mu_{SEP} = \mu_{PBO}$ versus H_1 : $\mu_{SEP} \neq \mu_{PBO}$

5. STUDY OBJECTIVES

5.1. Primary Objective

To evaluate the efficacy of flexibly dosed SEP-363856 (25, 50, or 75 mg/day) in subjects with PDP as measured by the Scale for Assessment of Positive Symptoms – Parkinson's Disease (SAPS-PD) at Week 6.

5.2. Secondary Objectives

Double-blind Period:

- To evaluate the efficacy of SEP-363856 (25, 50, or 75 mg/day) in subjects with Parkinson's Disease Psychosis as measured by:
 - Neuropsychiatric Inventory (NPI)
 - Clinical Global Impression Severity (CGI-S)
 - Mini Mental State Examination (MMSE) for cognition

5.3. Safety Objectives

Double-blind period:

- To evaluate the safety and tolerability of SEP-363856 (25, 50, or 75 mg/day) using:
 - Adverse event (AE) reports
 - Clinical laboratory results
 - 12-lead electrocardiograms (ECG)
 - Vital signs
 - Physical and neurological examinations (PE, NE)
 - Body weight, body mass index (BMI)
 - Columbia-Suicide Severity Rating Scale (C-SSRS)

Open Label Period:

- To further evaluate the safety and tolerability of open-label flexibly dosed SEP-363856 (25, 50, or 75 mg/day)
 - Adverse event (AE) reports
 - Clinical laboratory results
 - 12-lead electrocardiograms (ECG)
 - Vital signs
 - Physical and neurological examinations (PE, NE)
 - Body weight and body mass index (BMI)
 - Columbia Suicide Severity Rating Scale (C-SSRS)

5.4. Other Objectives

Double-blind Period:

- To evaluate the effects of SEP-363856 sleep quality as measured by the Scales for Outcomes in Parkinson's Disease for nighttime sleep quality (SCOPA-NS) and daytime sleepiness (SCOPA-DS).
- To evaluate the effects of SEP-363856 on motor symptoms associated with Parkinson's Disease as measured by the Unified Parkinson's Disease Rating Scale Parts 2 and 3 (UPDRS II and III).

To evaluate the effects of SEP-363856 on Rapid Eye Movement (REM) Sleep Behavioral Disorder (RBD) symptoms as measured by the RBD questionnaire (RBDQ).

Open Label Period:

- To further evaluate the effectiveness of flexibly-dosed SEP-363856 over 12-weeks of treatment using:
 - Neuropsychiatric Inventory (NPI)
 - Clinical Global Impression-Severity (CGI-S)
 - Mini Mental State Exam (MMSE)
 - SAPS-PD
- To evaluate the effects of SEP-363856 on sleep quality as measured by the Scales for Outcomes in Parkinson's disease for nighttime sleep quality (SCOPA-NS) and daytime sleepiness (SCOPA-DS).
- To evaluate the effects of SEP-363856 on motor symptoms associated with Parkinson's Disease as measured by the Unified Parkinson's Disease Rating Scale Parts 2 and 3 (UPDRS II and III).
- To evaluate the effects of SEP-363856 on Rapid Eye Movement (REM) Sleep Behavioral Disorder (RBD) symptoms as measured by RBD questionnaire (RBDQ).

6. STUDY ENDPOINTS

6.1. Primary Endpoint

The primary endpoint is the change from double-blind (DB) Baseline in total SAPS-PD score at Week 6.

6.2. Secondary Endpoints

Double Blind Period:

- Change from DB Baseline in the CGI-S at Week 6.
- Change from DB Baseline in NPI at Week 6.
- Change from DB Baseline in MMSE at Week 6.

6.3. Safety Endpoints

Double Blind Period:

- The incidence of AEs, SAEs, and AEs (or SAEs) leading to discontinuation during the double-blind period.
- Absolute values and changes from DB Baseline in clinical laboratory tests (hematology, serum chemistry, urinalysis), and clinical evaluations (vital signs, body weight, BMI, blood pressure [supine and standing], heart rate [supine and standing], and 12-lead ECGs).
- Frequency of subjects with suicidal ideation or suicidal behavior using the C-SSRS during the double-blind period.

Open-label period:

- The incidence of AEs, serious adverse events (SAEs), and AEs (or SAEs) leading to discontinuation during the open-label (OL) extension and overall.
- Absolute values and changes from DB and OL Baseline in clinical laboratory tests (hematology, serum chemistry, urinalysis), and clinical evaluations (vital signs, body weight, BMI, blood pressure [supine and standing], heart rate [supine and standing], and 12-lead ECGs).
- Frequency of subjects with suicidal ideation or suicidal behavior using the C-SSRS during the open-label extension and overall.

6.4. Other Endpoints

Double Blind Period:

- Change from DB Baseline in nighttime sleep quality as measured by the SCOPA-NS at Week 6.
- Change from DB Baseline in daytime sleepiness as measured by the SCOPA-DS at Week 6.

- Change from DB Baseline in the UPDRS II and III at Week 6.
- Change from DB baseline in RBD symptoms at Week 6 as measured by the RBDQ.

Open Label Period:

- Change from DB and OL Baseline in nighttime sleep quality as measured by the SCOPA-NS at Week 18.
- Change from DB and OL Baseline in daytime sleepiness as measured by the SCOPA-DS at Week 18.
- Change from DB and OL Baseline in the UPDRS II and III at Week 18.
- Change from DB and OL baseline in RBD symptoms at as measured by the RBDQ at Week 18.
- Change from DB and OL Baseline in the CGI-S at Week 18.
- Change from DB and OL Baseline in NPI at Week 18.
- Change from DB and OL Baseline in MMSE at Week 18.
- Change from DB and OL baseline in total SAPS-PD at Week 18.

7. INVESTIGATIONAL PLAN

[figure not shown]
7.1. Overall Study Design

This is a multicenter, randomized, parallel-group, placebo-controlled study evaluating the efficacy, safety, and tolerability of double-blind SEP-363856 flexibly dosed at 25, 50, or 75 mg/day for 6 weeks followed by 12 weeks of open-label extension SEP-363856 flexibly-dosed at 25, 50, or 75 mg/day in male and female subjects \geq 55 years of age with a clinical diagnosis of PDP. The study will randomize approximately 36 subjects to 2 treatment groups in a 2:1 ratio (approximately 24 subjects to SEP-363856 and 12 to placebo).

The study will consist of 4 periods: Screening/Washout Period (up to 14 days prior to Doubleblind Treatment), Double-blind Treatment Period (6 weeks), Open-label SEP-363856 Treatment Period (12 weeks), and Follow-up Period (1 week after last dose). All post-Baseline clinic visits will have a window of \pm 2 days relative to the date of the Baseline visit (Visit 3).

A study schematic is presented in Figure 1. Details of the study assessments and other procedures to be performed at each visit are presented in Table 2 and Table 3, Schedule of Assessments, and Section 11, Study Assessments. If necessary, subjects may return to the clinic at any time for an unscheduled visit.

Figure 1: Study Schematic

Note: Double-blind ends with Day 43 assessments; Open-label extension begins Day 43 with first dose in the evening.

Screening/Washout Period (Days -14 to -1):

Subjects who provided written informed consent to participate in the study will be evaluated for eligibility during a screening/washout period of up to 14 days, during which they will be tapered off all antipsychotic or centrally acting anticholinergic medications in a manner that is consistent with labeling recommendations and conventional medical practices. The subject's caregiver must also provide consent for the subject to participate in this study as well as consent for collection of caregiver data as related to the assessment of the subject's neuropsychiatric status as measured by the NPI. The screening visit may occur over more than one day. The washout period can start immediately at screening. Prior treatment with antipsychotic agents must be discontinued at least 5 half-lives prior to the site performing the NPI and MMSE screening assessments.

Subjects who meet the study entry criteria at screening (see inclusion criteria in Section 8.1) and have gone through the washout period, as necessary, will enter the 6-week double-blind treatment period.

Double-blind Treatment Period (6 weeks):

Randomization/Treatment:

[figure not shown]
At Baseline (Day 1, Visit 3), subjects who have successfully completed screening/washout (see randomization criteria in Section 8.3) will be randomly assigned via interactive voice/web response system (IXRS) in a 2:1 ratio to SEP-363856 or placebo. Study drug dosing will begin following completion of the baseline assessments on the same day (Day 1, Visit 3). Double-blind study drug will be taken in-clinic at the Baseline visit (Day 1) and on visit days when subject titrates up. Subsequent doses starting the following day should be taken at bedtime. For the remainder of the study, subjects will take one capsule of study drug per day at approximately the same time each evening at bed-time. After receiving the initial dose (Day 1) and after each up-titration, subjects will remain in the clinic for 2 hours of clinical observation, which will include assessments of orthostatic vital signs (1 hour [± 15 min] and 2 hours [± 15 min] post dose), additional medical assessments can be performed as needed per investigator discretion. Findings will be collected on appropriate case report forms (CRFs). Subjects will be discharged home if medically stable. Dosing will continue QD at bedtime for the remainder of the study, without regard for food.

Subjects will have clinic visits and procedures as outlined in Table 2. Telephone calls to the subjects will be made on the first 2 days after a dose adjustment. An unscheduled visit will be made as early as possible for dose adjustments or evaluation of safety/tolerability issues. Efforts will be made to ensure that the subject's caregiver remains the same for all study visits. All post-Baseline clinic visits will have a window of \pm 2 days relative to the date of the Baseline visit (Visit 3).

Subjects randomized to SEP-363856 will receive flexible doses of SEP-363856 (25, 50, or 75 mg/day). Subjects will receive SEP-363856 25 mg/day for 1 week (Days 1 - 7). If there are no safety or tolerability issues, subjects should be up-titrated to 50 mg/day at Visit 4 (Week 2). Subjects still receiving SEP-363856 25 mg/day must have their dose up-titrated to 50 mg/day at Visit 5 (Week 3), unless approved to stay at 25 mg/day by the Medical Monitor due to safety and tolerability concerns. At the investigator's discretion, subject may up-titrate to 75 mg during scheduled visits. During the double-blind period up-titration will not be allowed after Visit 6 (Week 5). Dose reductions to 50 mg/day or 25 mg/day will be allowed by 1 dose level, at any

time for reasons of safety and tolerability. During the double-blind period, following a dose reduction, subjects may increase their dose to the next dose level up to Visit 6 (Week 5) at the Investigator's discretion and only during scheduled visits. If safety or tolerability issues result in study medication dose discontinuation or reduction, the Investigator must contact the Medical Monitor before the subject is rechallenged. The study medication can be re-introduced if agreed to by the Investigator and Medical Monitor.

Figure 2: Dosing Schematic

Notes:

- Dose reduction is allowed at any time for reasons of safety or tolerability; during unscheduled or scheduled visits.
- During the Double-Blind Period, up-titration to a prior dose level is allowed at Investigator's discretion and only during a scheduled visit.
- At Visit 5 (Week 3), the dose should be up titrated to 50mg/day. In the event of tolerability/safety concerns, the dose may remain at 25 mg/day with Medical Monitor approval.
- Visit 6 (Week 5) is the last visit where up-titration can occur during the Double-Blind Period.

Open-label Extension Period:

For subjects who complete the DB period and continue into the Open-label (OL) period, the baseline visit for the open-label period will be the end of double-blind treatment period (Week 6 of DB period). Drug will be taken in-clinic on OL Day 1 (Study Day 43) of the open-label period and on study visit days when subject up- titrates; with subsequent dosing starting the following day at bedtime. For the remainder of the study, subjects will take one capsule of study drug per day at approximately the same time each evening at bedtime. After receiving the initial dose of 25 mg (OL Day 1) and after each up-titration, subjects will remain in the clinic for 2 hours of clinical observation; which will include assessments of orthostatic vital signs (1 hour [± 15 min] and 2 hours [± 15 min] post dose); additional medical assessments can be performed as needed per investigator discretion. Findings will be collected on appropriate case report forms (CRFs).

Subjects will be discharged home if medically stable. Dosing will continue once daily (QD) at bedtime for the remainder of the study, without regard for food.

The total daily dose will remain between 25 mg/day and 75 mg/day for the 12-week treatment period. Subjects will receive SEP-363856 25 mg/day for 1 week. If there are no safety or tolerability issues, subjects should be up-titrated to 50 mg/day at Visit 8 (OL Week 2; OL Day 8). Subjects still receiving SEP-363856 25 mg/day must have their dose up- titrated to 50 mg/day at Visit 9 (OL Week 3), however may remain at 25 mg/day due to safety/tolerability issues with medical monitor approval. At the investigator's discretion, subject may up-titrate to 75 mg during scheduled visits.

Dose reductions will be allowed by 1 dose level, at any time for reasons of safety and tolerability. Following a dose reduction, subjects may increase their dose at the Investigator's discretion and only during scheduled visits. If safety or tolerability issues result in study medication dose discontinuation or reduction, the Investigator must contact the medical monitor before the subject is re-challenged. The study medication can be re-introduced if agreed on by the Investigator and Medical Monitor.

A minimum of 7 days is required between dose increases. Dose decreases may be made at any time, at the Investigator's discretion, for reasons of safety or tolerability. If, in the judgment of the investigator, the subject does not tolerate the minimum required dose (25 mg/day), the subject will be discontinued from the study.

During the OL extension treatment period, subjects will return to the clinic and have assessments as described in Table 3.

Telephone calls to the subjects will be made on the first 2 days after a dose adjustment (increase or decrease). At Study Week 12 and Study Week 16 (midpoint between Visit 11 and Visit 12, and midpoint between Visit 12 and Visit 13) the site staff will contact the subject via telephone in order to monitor for AEs, SAEs, and concomitant medications, as well as to remind subjects about adherence to study drug administration, and upcoming visits. If necessary, an unscheduled visit will be made as early as possible for dose adjustments or evaluation of safety/tolerability issues.

Follow-up Period (7 days):

All subjects who either complete the treatment period or discontinue early will have a follow-up visit for final safety assessments 7 days (\pm 2 days) after the last dose of study drug.

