 - Neuropsychiatric Inventory (NPI)
 - Clinical Global Impression-Severity (CGI-S)
 - Mini Mental State Exam (MMSE)
 - SAPS-PD
- To evaluate the effects of SEP-363856 on sleep quality as measured by the Scales for Outcomes in Parkinson's disease for nighttime sleep quality (SCOPA-NS) and daytime sleepiness (SCOPA-DS).
- To evaluate the effects of SEP-363856 on motor symptoms associated with Parkinson's Disease as measured by the Unified Parkinson's Disease Rating Scale Parts 2 and 3 (UPDRS II and III).
- To evaluate the effects of SEP-363856 on Rapid Eye Movement (REM) Sleep Behavioral Disorder (RBD) symptoms as measured by RBD questionnaire (RBDQ).

Study Design:

This is a multicenter, randomized, parallel-group, placebo-controlled study evaluating the efficacy, safety, and tolerability of double-blind SEP-363856 flexibly dosed at 25, 50, or 75 mg/day for 6 weeks followed by 12 weeks of open-label extension of SEP-363856 flexibly-dosed at 25, 50, or 75 mg/day in male and female subjects ≥ 55 years of age with a clinical diagnosis of PDP. The study will randomize approximately 36 subjects to 2 treatment groups in a 2:1 ratio (approximately 24 subjects to SEP-363856 and 12 to placebo).

The study will consist of 4 periods: Screening/Washout Period (up to 14 days prior to Double-blind Treatment), Double-blind Treatment Period (6 weeks), Open-label SEP-363856 Treatment Period (12 weeks), and Follow-up Period (1 week after last dose) as shown in the following figure. All post-Baseline clinic visits will have a window of \pm 2 days relative to the date of the Baseline visit (Visit 3).

Note: Double-blind ends with Day 43 assessments; Open-label extension begins Day 43 with first dose in the evening.

Screening/Washout Period (Days -14 to -1):

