9.4. Dispensing of Study Drug

An interactive voice/web response system (IXRS) will be used to manage subject screening and randomization. The IXRS is an integrated web-based subject and drug management system.

Study drug blister cards will be assigned by the IXRS based on the treatment schedule and dose adjustment criteria. The IXRS will generate instructions for which study medication unit/number to assign to a subject. Each subject will be dispensed one to four 9-day blister cards per scheduled visit depending on the timing of the next scheduled visit (see Table 2 and Table 3).

Study drug will be taken in-clinic at the Double-blind Baseline visit (Day 1), at Open-label baseline Visit 7 (Day 43; OL Day 1), and on visit days when subject titrates up; with subsequent dosing starting the following day at bedtime. For the remainder of the study, subjects will take one capsule of study drug per day at approximately the same time each evening at bedtime. Study drug may be taken without regard for food.

Study drug should be maintained under the strict control of qualified site staff at all times. Appropriate guidelines should be followed in proper dispensation to the study participant. Proper handling and storage should be followed. IXRS drug dispensing guidelines should be followed for dispensing study drug to the subject, in addition to all accountability records where required. Blister card opening instructions should be reviewed with the subject at time of dispensation. Specific User Manuals will be supplied.

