10. TREATMENT OF SUBJECTS

10.1. Study Drug

Active and matched placebo doses (study drug) will be administered QD daily during the double-blind treatment period. Double-blind study drug (active or matched-placebo, as applicable) dosing will be taken in-clinic at Visit 3 (Day 1) and Visit 7 (Day 43; OL Baseline Day 1); as well as on visit days when a subject up-titrates. Subsequent doses starting the following day should be taken at bedtime. For the remainder of the study, subjects will take one capsule of study drug per day at approximately the same time each evening at bedtime.

All study drug doses will consist of capsule(s) containing either SEP-363856 or matched placebo (in order to maintain blinding) administered orally QD.

Subjects may take study drug without regard for food.

Blood samples for determination of plasma SEP-363856 and SEP-363854 concentrations will be collected predose (before study drug administration) and postdose as describe in Table 2 and Table 3 as well as in Section 22. The time and date of the 3 previous doses of study drug, time, and date of sampling must be recorded. The time and date of food intake will be recorded on Day 43 when blood samples are collected for determination of plasma SEP-363856 concentrations.

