10.1.1. Dosage Adjustment Criteria

During the DB treatment period:

Subjects randomized to SEP-363856 will receive flexible doses of SEP-363856 (25, 50, or 75 mg/day). Subjects will receive SEP-363856 25 mg/day for 1 week (Days 1 - 7). If there are no safety or tolerability issues, subjects should be up-titrated to 50 mg/day. Subjects still receiving SEP-363856 25 mg/day must have their dose up-titrated to 50 mg/day at Visit 5 (Week 3). At the investigator's discretion, subject may up-titrate to 75 mg during scheduled visits. Up-titration will not be allowed after Visit 6 (Week 5). Dose reductions will be allowed by 1 dose level, at any time for reasons of safety and tolerability. Following a dose reduction, subjects may increase their dose to the next dose level up to Visit 6 (Week 5) at the Investigator's discretion and only during scheduled visits. If safety or tolerability issues result in study medication dose discontinuation or reduction, the Investigator must contact the medical monitor before the subject is re-challenged. The study medication can be re-introduced if agreed on by the Investigator and Medical Monitor.

Subjects randomized to placebo will receive placebo treatment throughout the study.

During the OL extension treatment period:

Subjects will receive flexible doses of SEP-363856 (25, 50, or 75 mg/day). Subjects will receive SEP-363856 25 mg/day for 1 week. If there are no safety or tolerability issues, subjects should be up-titrated to 50 mg/day at Visit 8 (OL Week 2; OL Day 8). Subjects still receiving SEP-363856 25 mg/day must have their dose up-titrated to 50 mg/day at Visit 9 (OL Week 3). At the investigator's discretion, subject may up-titrate to 75 mg during scheduled visits. Dose reductions will be allowed by 1 dose level, at any time for reasons of safety and tolerability. Following a dose reduction, subjects may increase their dose at the Investigator's discretion and

only during scheduled visits. If safety or tolerability issues result in study medication dose discontinuation or reduction, the Investigator must contact the medical monitor before the subject is re-challenged. The study medication can be re-introduced if agreed on by the Investigator and Medical Monitor.

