If subject appears to be symptomatic as assessed by the site during a telephone contact, an unscheduled visit will be made as early as possible (see Section 11.9.12).

11.9.4. Visit 7 (Study Day 43 [± 2 days], Open-label Baseline, OL Day 1)

The following procedures will be conducted during this visit:

- Prior/concomitant medications
- Study drug accountability
- Dispense Study Drug
- Physical and neurological examination
- Weight
- Vital sign measurements (prior to ECG)
- Perform standard 12-lead ECG
- Blood samples for clinical laboratory evaluation (hematology, serum chemistry, serum prolactin, HbA_{1c}, glucose panel, and lipid panel)
- Urine sample for urinalysis and urine drug screen
- Blood sample for determination of plasma SEP-363856 and SEP-363854, 12 ± 4 hours after the Day 42 dose
- Perform breath alcohol test
- SAPS-PD
- NPI
- CGI-S
- MMSE
- UPDRS II and UPDRS III
- SCOPA-DS
- SCOPA-NS
- RBDQ

- C-SSRS
- Adverse events
- Review Continuation Criteria for Open-label extension
- Administer first open-label study drug dose

After receiving the initial dose of OL study drug, subjects will remain in the clinic for at least 2 hours of clinical observation, which will include periodic assessments of orthostatic vital signs (1 hour [\pm 15 min] and 2 hours [\pm 15 min] post dose); additional medical assessments can be performed as needed per investigator discretion. Findings will be collected on appropriate case report forms (CRFs). Subjects will be discharged home if medically stable. Telephone calls to the subjects will be made on the first 2 days following the visit (see Section 11.9.11).

11.9.5. Visit 8 (Day 50 ± 2 days; OL Day 8),

The following procedures will be conducted during this visit:

- Concomitant medications
- Study drug accountability
- Dispense Study drug
- Vital sign measurements (prior to ECG)
- NPI
- CGI-S
- MMSE
- UPDRS II and UPDRS III
- C-SSRS
- Adverse events

If the subject titrates up, the subject will remain in the clinic for at least 2 hours of clinical observation, which will include periodic assessments of orthostatic vital signs (1 hour [\pm 15 min] and 2 hours [\pm 15 min] post dose); additional medical assessments can be performed as needed per investigator discretion.

A telephone calls to the subjects will be made on the first 2 days after a dose adjustment (increase or decrease) (see Section 11.9.11).

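### The schematic note puts the first open-label dose in the evening of Day 43, against the in-clinic, observed dose at Visit 7 elsewhere in the protocol

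*Protocol*

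**What the plan says.** The protocol times the first open-label dose in two ways.

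- **Evening.** The schematic note in Section 7.1 reads "Double-blind ends with Day 43 assessments; Open-label extension begins Day 43 with first dose in the evening". The Synopsis carries the same note. It gives a time of day, but no place and no observation.
- **In clinic at Visit 7.** The Open-label Extension paragraph of Section 7.1 states "Drug will be taken in-clinic on OL Day 1 (Study Day 43) of the open-label period" and continues "After receiving the initial dose of 25 mg (OL Day 1) and after each up-titration, subjects will remain in the clinic for 2 hours", with orthostatic vital signs at 1 h and 2 h. The Synopsis says the same. Section 9.4 has the drug taken in clinic "at Open-label baseline Visit 7 (Day 43; OL Day 1), and on visit days when subject titrates up", and footnote c to Tables 2 and 3 agrees. All four places start bedtime dosing on the following day. Footnote e requires vital signs 1 h and 2 h after the Visit 7 dose. Section 11.9.4 lists the first open-label dose as a Visit 7 procedure and adds "After receiving the initial dose of OL study drug, subjects will remain in the clinic for at least 2 hours of clinical observation".

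Two further sentences are loosely worded. Section 10.1 says "Double-blind study drug (active or matched-placebo, as applicable) dosing will be taken in-clinic at Visit 3 (Day 1) and Visit 7 (Day 43", although the same parenthesis goes on to label the visit as the open-label baseline. Section 10.1.1 says "Subjects randomized to placebo will receive placebo treatment throughout the study", under its double-blind heading. Section 7.2.2 has every subject receive unblinded SEP-363856 once the double-blind period is over.

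**The concern.** For a subject randomized to placebo, the first open-label dose is the first exposure to SEP-363856. The protocol treats first exposure with caution. Section 7.3.2 says the drug had not been given to patients with Parkinson's disease or its psychosis before this study. Section 7.3.1 says there are no data in patients aged 65 or over. Section 4.3 reports a hypotension event in a healthy volunteer that was assessed as serious. The 2 h observation with two orthostatic readings is the planned safeguard for this dose.

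A dose taken in the evening after discharge would lose that safeguard. A site that reads the schematic note literally has a basis in the protocol for doing this.

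**Working it through.** No figure in the plan needs reproducing. The check sets the passages side by side, then asks whether the two timings could describe a single event.

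**1. What each place says about the Day 43 dose**

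| Place in the protocol | Drug | Where and when | Post-dose check |
|---|---|---|---|
| Schematic note (Synopsis, 7.1) | Open-label, dose level not given | Evening; place not given | None mentioned |
| Open-label Extension text (Synopsis, 7.1) | Open-label, 25 mg | In clinic; bedtime from next day | 2 h observation, orthostatic vital signs at 1 h and 2 h |
| Footnote c | Study drug | In clinic, Visit 7; bedtime from next day | Not covered |
| Footnote e | Not stated | Visit 7 | Vital signs at 1 h and 2 h |
| Section 9.4 | Study drug | In clinic, Visit 7; bedtime from next day | Not covered |
| Section 11.9.4 | Open-label, dose level not given | Procedure of Visit 7 | At least 2 h observation, orthostatic vital signs at 1 h and 2 h |
| Section 10.1 | Described as double-blind | In clinic, Visit 7; bedtime from next day | Not covered |

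Only the Open-label Extension text gives the 25 mg dose, the observation and the orthostatic readings together. The other entries each support part of it.

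**2. Could both be true, as an evening dose taken in clinic?**

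Footnote h and Section 11.9.4 place the Visit 7 pharmacokinetic sample 12 ± 4 h after the Day 42 dose:

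- earliest: 12 − 4 = 8 h
- latest: 12 + 4 = 16 h

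The Day 42 dose is a bedtime dose. The protocol gives no clock time for bedtime, so I assume a range from 20:00 to 24:00.

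| Assumed bedtime, Day 42 | Sample window, Day 43 |
|---|---|
| 20:00 | 04:00 to 12:00 |
| 22:00 | 06:00 to 14:00 |
| 24:00 | 08:00 to 16:00 |

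Under these bedtimes the subject has to be at the site no later than some time between 12:00 and 16:00. An evening dose in clinic would then need a long stay or a second attendance on the same day, and no passage describes either. The in-clinic text also makes Day 43 the exception to bedtime dosing, because bedtime dosing starts the day after. The joint reading is therefore not natural.

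**3. How many subjects**

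Section 15.1 plans about 36 subjects randomized 2:1, so 36 × 1/3 = 12 on placebo. This is an upper bound. Continuation under Section 8.4 requires completing the double-blind period and meeting three further criteria.

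**4. The two secondary sentences**

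- Section 10.1 describes the Visit 7 dose as double-blind drug. Footnote a puts the last double-blind dose on the day before the Day 43 visit, and Section 11.9.4 calls the Visit 7 dose open-label.
- The placebo sentence in Section 10.1.1 is at odds with Section 7.2.2 if read literally. Its heading limits it to the double-blind period, and the open-label instruction follows directly.

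**The case against.** The strongest reply is that a site works from its visit checklist and not from a figure note. The paragraph introducing Figure 1 sends the reader to Tables 2 and 3 and Section 11 for visit procedures, and those put the dose and the post-dose checks at Visit 7. The note states no place, so sending the subject home to dose is an inference. A further note under Table 3 keeps subjects on site at Visit 7 until the investigator discharges them, and Section 11.9.11 requires telephone calls on the next two days.

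Much of this stands. It makes an unobserved dose unlikely at a site that follows Section 11.9.4, and it shows what the detailed schedule intends. It does not remove the contradiction, which is in current text and appears twice. The calls cover adverse events and medications, so they do not replace orthostatic readings at 1 h and 2 h.

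A reader might draw three stronger conclusions, which the documents do not support:

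- **That Section 10.1 is a competing instruction under which a placebo capsule could be given on open-label Day 1.** Its own parenthesis names the open-label baseline, footnote a has double-blind dosing finished the day before, and Section 9.4 has the IXRS assign the blister cards. This is loose wording.
- **That the split between double-blind and open-label adverse events becomes ambiguous.** SAP Section 16.1 divides events at the actual first open-label dose, using clock time where available. The rule is the same whichever timing a site follows.
- **That the conflict creates an exposure problem, with a 25 mg clinic dose soon after a bedtime dose of up to 75 mg.** That concerns subjects already on active drug, not the placebo subjects at issue. Similarly close spacing arises from the in-clinic dosing prescribed on every up-titration day.

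**Conclusion.** The concern holds as an internal contradiction about the time and setting of one dose, with a possible safety consequence. The schematic note cannot comfortably be reconciled with in-clinic dosing and post-dose observation at Visit 7. If a site followed the note, placebo subjects who continue, at most about 12 of 36, could take their first active dose without either planned orthostatic check. Most operational passages point to the clinic, so this is a risk created by the wording, not the expected course.

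The size rests on the planned 2:1 allocation and on every placebo subject continuing. The judgement that an evening dose in clinic is unnatural rests on the assumed bedtimes of 20:00 to 24:00 and on the absence of any passage describing an evening stay or a return. The double-blind label in Section 10.1 and the placebo sentence in Section 10.1.1 are secondary drafting faults. The primary efficacy analysis is not affected. Which instruction should apply is for the sponsor to decide.

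**What to change.** The sponsor should reconcile these passages to one Day 43 instruction stating the drug, place, time and observation. That instruction should appear identically in:

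- the schematic note, in both the Synopsis and Section 7.1;
- the Open-label Extension text of the same two sections;
- footnotes c and e to Tables 2 and 3;
- Sections 9.4, 10.1 and 11.9.4.

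The double-blind description of the Visit 7 dose in Section 10.1 and the placebo sentence in Section 10.1.1 should be aligned with it and with Section 7.2.2. A clarification letter should go to the sites.

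The cost is a wording amendment and one letter. No visit, procedure or analysis is added.
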